8.2.1.2.2 Procedure for Reporting a Serious Adverse Event

For a SAE occurring during the period of the clinical study, regardless of whether it is related to the treatment or not, and of whether it is expected or not, the Investigator must do the following:

- 1. Take prompt and appropriate medical action, if necessary. The safety of the subject is the first priority.
- 2. Ensure that the event is classified as an SAE (Section 8.2.1.1.3).
- 3. Complete the AE form provided in the eCRF as fully as possible.

Print and complete the SAE form. E-mail the completed form, accompanied by any other relevant information or anonymized medical records (e.g., laboratory test results) within 24 hours of receipt of the information to the Safety Mailbox listed below. The demographics, medical history, drugs/therapies form, medical and surgical procedures form, and AE pages of the eCRF must be completed and available for review in the EDC system at the time of the report.

4. Immediately send the completed SAE report form to the Safety Mailbox via e-mail and discuss further actions to be taken.

- 5. Monitor and record the progress of the event until it resolves or reaches a clinically stable outcome, with or without sequelae. For all additional follow-up evaluations, send by e-mail all additional follow-up information on the SAE to the Safety Mailbox within 24 hours of receipt of the updated information. SAEs will be monitored until the Investigator and Sponsor agree that the event is satisfactorily resolved.
- 6. Obtain and maintain in his/her files all pertinent medical records, information, and medical judgments from colleagues who assisted in the treatment and follow-up of the subject. If necessary, contact the subject's personal physician or hospital staff to obtain further details.

- 7. Inform the Sponsor of the final outcome of the event. Send a revised or updated SAE form and AE form, if appropriate to the Safety Mailbox.
- 8. Prompt notification of SAEs by the Investigator to the Sponsor is essential so that legal obligations and ethical responsibilities towards the safety of subjects are met. The Sponsor has a legal responsibility to notify both the local regulatory authority and other regulatory agencies about the safety of a product under clinical investigation. The Sponsor will comply with country specific regulatory requirements relating to safety reporting to regulatory authorities, Institutional Review Boards (IRBs), and Investigators. Investigator safety reports are prepared for Suspected Unexpected Serious Adverse Reactions (SUSARs) according to local regulatory requirements and the Sponsor policy and are forwarded to Investigators as necessary. An Investigator who receives an Investigator safety report describing a SAE(s) or other specific safety information (e.g., summary or listing of SAEs) from the Sponsor will file it with the prescribing information and will notify the IRB, if appropriate according to local requirements.
- 9. Comply with the applicable regulatory requirement(s) related to the reporting of SAEs to the IRB.

8.2.1.2.3 Procedures for Reporting Pregnancies

Any pregnancy occurring during the clinical study, where the fetus could have been exposed to the study product, must be monitored until its outcome in order to ensure the complete collection of safety data.

Pregnancies occurring during the screening period are considered as screening failures; they are recorded as such in the eCRF and no pregnancy form is to be completed.

If a subject becomes pregnant after the screening period, the Investigator is to do the following:

- 1. The subject does not need to be withdrawn from the clinical study, i.e. she may continue to attend the planned study visits, but no invasive procedure should be conducted (e.g. no sample taken for lab test).
- 2. Complete the Pregnancy Surveillance form Part I: History and Start of Pregnancy, as fully as possible. Send by e-mail this pregnancy form along with the exit form (if applicable) within 24 hours of receipt of the information to the Safety Mailbox listed above (see Section 8.2.1.2.2).
- 3. Monitor and record the progress of the pregnancy until its outcome. Contact the subject's regular physician (general practitioner or gynecologist) or hospital staff to obtain further details and ask regular follow-up information.
- 4. Inform the Sponsor of the progress by tri-monthly updates until the final outcome of the pregnancy by completing the Pregnancy Surveillance form Part I. For all the additional evaluations, send by e-mail the additional follow-up information to the Safety Mailbox within 24 hours of receipt of the information. If the subject can no longer be reached (lost to

follow-up), documentation of the non-response/contact with two phone calls and a letter (certified with return receipt) is required.

- 5. At the outcome of the pregnancy, complete the Pregnancy Surveillance form Part II: Course and Outcome of Pregnancy, as fully as possible. Inform the Sponsor by sending this pregnancy form to the Safety Mailbox within 24 hours of receipt of the information.
- 6. If the pregnancy leads to an abortion (voluntary abortion, spontaneous abortion or therapeutic abortion), *in utero* death or congenital anomaly, follow the procedure for declaration of an SAE (see Section 8.2.1.2.2).

Pregnancy Test

For all women of childbearing potential a urine pregnancy test will be performed prior to treatment at screening/baseline and month 6, and month 12 (if optional re-treatment is performed). A negative pregnancy test is required for study inclusion. The result will be documented.

8.4 Appropriateness of Measurements

The subject satisfaction question and questionnaire are tools that have been developed in order for the Sponsor to better understand the subject's needs and expectations with respect to abobotulinumtoxinA treatment and the treatment regimen.

[figure not shown]

[figure not shown]
9 CLINICAL STUDY VISITS DESCRIPTIONS AND PROCEDURES

[figure not shown]
9.1 Description of Clinical Study Visits

[figure not shown]
Please refer to the schedule of assessment table (Table 2).

[figure not shown]
A written, signed ICF (inclusive of HIPAA and photo consent) must be obtained prior to performing any clinical study-related evaluations and/or procedures. The subject must be provided with a fully completed, dated and signed copy.

[figure not shown]

	M study	
👶 GALDERMA	, i study	

10 STATISTICAL METHODS PLANNED

	1	
	8	
		_

10.1.2.4 Safety Population

The safety population includes all subjects who were administered the study product.

10.1.2.5 Imputation of Missing Data

All analyses will be carried out based on the observed cases (OC). However, if there are a substantial amount of missing data for the primary efficacy endpoint, a sensitivity analysis to assess the impact of the missing data might be done by using, for example, the hot deck method.

10.1.3 Data Presentation and Graphics

Subject disposition, completion and discontinuation by study visit, protocol deviations, demographics and baseline characteristics, medical history, medical and surgical procedures, prior and concomitant medications, will be summarized.

All efficacy variables will be summarized by visit.

10.1.3.1 Safety

A summary of all AEs will be provided, which will include:

- number of subjects who did not have an AE
- number of subjects with at least one AE and number of events
- number of subjects with at least one TEAE and number of events
- number of subjects with at least one related TEAE and number of events
- number of subjects with at least one TEAE by causality
- number of subjects with at least one TEAE by maximum intensity
- number of subjects with at least one TEAE leading to discontinuation
- number of subjects with at least one serious TEAE.

All TEAEs, treatment emergent SAEs, TEAEs by maximum intensity, TEAEs by causality, TEAEs by maximum intensity and causality, and TEAEs leading to discontinuation will be summarized

by SOC and PT including number of subjects with at least one event, percentages, and number of events. All related TEAEs will also be summarized by time to onset and duration.

The results of the urine pregnancy tests will be listed.

10.1.4 Withdrawals and Deviations

All withdrawn subjects will be listed individually, including at least subject number, date and reason for withdrawal, and last visit performed.

10.2 Sample Size Determination

🕹 GALDERMA	43USD1802 Clinical Study Protocol Dysport DREAM study	
10.3		

11 TRAINING / MONITORING / DATA MANAGEMENT / QUALITY ASSURANCE

11.1 Personnel Training

Investigators and other responsible persons should be listed together with their function on the delegation log. Study staff shall provide a curriculum vitae or equivalent, as appropriate.

It is the responsibility of the PI to ensure that all personnel involved in the study are fully informed of all relevant aspects of the study, including detailed knowledge of and documented training in all procedures to be followed.

11.2 Clinical Monitoring

The conduct of the clinical study will be closely monitored by representatives of the Sponsor to verify adherence to the clinical study protocol, ICH-GCP guidelines, and applicable SOPs.

The Investigator will allow the CRO/Sponsor's representatives, to have direct access to all clinical study records, CRFs, corresponding subject medical records, study product(s) dispensing records, and any other documents considered source documentation. Additionally, the CRO/Sponsor representative is to have access to the study product storage area and clinical study facilities.

The Investigator also agrees to assist the representative if required.

11.3 Data Management

All data management procedures will be detailed in a Data Management Plan (DMP).

11.4 Quality Assurance / Audit / Inspection

The clinical study is conducted under the sponsorship of the Sponsor in compliance with the applicable international and local regulatory requirements as well as applicable ICH guidelines and in accordance with the SOPs for clinical study conduct and monitoring from the Sponsor and/or the Contract Research Organization (CRO).

Audits of clinical study centers may be conducted by the Sponsor/CRO representatives, and inspection may be performed by Regulatory Authority inspectorates or IRBs/IECs before, during, or after the clinical study.

The Investigator will allow and assist the CRO/Sponsor's representatives, IRBs/IECs and any regulatory agency to have direct access to all requested clinical study-related records.

For the audits performed by, or on behalf of, the Sponsor auditors, audit certificate(s) will be provided by Quality Assurance.

11.5		

12 ETHICS AND GENERAL CLINICAL TRIAL CONDUCT CONSIDERATIONS

12.1 Institutional Review Board (IRB)

This clinical study protocol and all amendments will be reviewed and approved by the appropriate IRBs.

12.2 Ethical Conduct of the Clinical Study

This clinical study will be conducted in accordance with the protocol, the HELSINKI declaration (1964) and subsequent amendments, and the ICH GCP, and in compliance with applicable regulatory requirements.

12.3 Subject Information and Consent

All subjects who participate in this clinical study are required to be fully informed about the clinical study in accordance with GCPs guidelines, federal regulations, HIPAA, and guidelines and in accordance with local requirements.

The ICF (inclusive of HIPPA and photo consent), approved by an IRB/IEC, will be fully explained to the subject. The subject must agree to photo consent in order to participate in the clinical study.

Prior to enrollment into the clinical study, the subject and the PI or designee must sign and date the consent form(s). The Investigator is responsible for maintaining each subject's consent form(s) in the Investigator's site file and providing each subject with a copy of the signed and dated consent form(s).

12.4 Protection of Personal Data

The completion of the study involves the gathering and processing of Personal Data as specified in the Regulation (EU) 2016/679 on the protection of individuals with regard to the processing of personal data and on the free movement of such data. For the purposes of the study, Sponsor will be considered the Data Controller, and Principal Investigator and Institution will both be considered Data Processors.

All processing of Personal Data must be carried out in accordance with national legislation concerning the protection of Personal Data. The Institution and Principal Investigator are responsible for complying with all requirements pursuant to national legislation in the country in which the Institution and Principal Investigator are located.

The Sponsor shall, to the extent feasible, protect study subject identifier information.

The Institution and Principal Investigator are jointly responsible for obtaining the appropriate informed consent of each subject for the processing of Personal Data required in order to complete

the study. Such consent shall include the consent to the transfer of Personal Data to government authorities located in countries outside the US.

The Institution and Principal Investigator are jointly responsible for providing sufficient information to all subjects to enable them to give their informed consent not only to the participation in the study, but also to the processing of Personal Data. Such information includes information regarding the purposes of the processing, the length of time during which Personal Data will be stored, the right of access to stored Personal Data and the right to correction or purging of incorrect or obsolete Personal Data. A subject may also withdraw his or her consent at any time. A subject who withdraws his or her consent to the processing of Personal Data must be considered to have withdrawn from the study but the data collected until the consent was withdrawn may be used in the statistical analyses.

All collection, processing and analyses of protected health information, personal data or similar will be conducted in compliance with applicable local, national and international rules, regulations and guidelines.

12.5 Contractual Requirements

A contractual agreement will be signed between the CRO/Sponsor and each Investigator/Institution. This document will contain supplementary information, including financial terms, confidentiality, the clinical study schedule, third party responsibility, and publication rights.

12.6 Data Collection and Archiving

12.6.1 Data Collection

The Investigator must maintain all required records for all subjects. Data for this clinical study will be recorded in the subject's source documents and in the eCRFs provided by the Sponsor. All data should be recorded in the eCRFs completely and promptly.

12.6.2 Source Documentation

The Investigator must keep accurate separate records (other than the eCRFs) of all subject visits, being sure to include all pertinent clinical study-related information. A statement should be made indicating that the subjects have been included in this clinical study and have provided signed written Informed Consent. All AEs must be thoroughly documented.

Results of any diagnostic tests conducted during the clinical study should also be included in the source documentation.

12.6.3 Archives

All pertinent data, samples, photographs, correspondence, and reports, the original or amended clinical study protocol, and all other material relating to the clinical study will be maintained securely in Sponsor/CRO/Investigator/Institution archives for the legally required duration for archiving.

The Investigator/Institution should maintain the essential clinical study documents as specified in Section 8 of ICH-GCP, and according to the applicable regulatory requirements.

[figure not shown]
The Investigator/Institution should take measures to prevent accidental or premature destruction of these documents.

If the Principal Investigator retires, relocates, or withdraws from the responsibility of keeping the clinical study records for any other reasons, custody must be transferred to a person who will accept the responsibility. The Sponsor/CRO must be notified in writing of the name and address of the new custodian.

12.7 Insurance

A certificate attesting Third Party coverage of CRO/Sponsor will be provided upon request.

^a Defining the role of authors and contributors, compiled by the International Committee of Medical Journal Editors (ICMJE) (http://www.icmje.org).

1.1 Background

This statistical analysis plan (SAP) describes the analysis variables and statistical procedures that will be used to analyze and report the results from Protocol 43USD1802 (v2.0), dated 03 AUG 2018.

The SAP was written in accordance with the recommendations outlined in the International Conference on Harmonisation (ICH) E9 Guideline entitled “Guidance for Industry: Statistical Principles for Clinical Trials” and the ICH-E3 Guideline entitled “Guidance for Industry: Structure and Content of Clinical Study Reports”.

1.1.1 Study Design

This is a multicenter, open-label, interventional, phase 4 study to assess subject satisfaction with a twice-yearly abobotulinumtoxinA treatment regimen in moderate to severe glabellar lines.

Following the screening process, eligible subjects will be treated at the baseline visit with abobotulinumtoxinA in the glabellar region.

The planned clinical study duration (from first subject first visit to last subject last visit) is approximately 15 months. Clinical study participation for each subject is up to 13 months.

1.1.2 Number of Subjects

The study is planned to enroll approximately at approximately 6 centers in the United States.

1.2 Study Objectives

1.2.1 Primary Efficacy Objective

The primary objective of the study is to evaluate subject satisfaction after abobotulinumtoxinA treatment every six months (twice yearly) using the proportion of subjects satisfied (“highly satisfied” or “satisfied”) with the treatment results assessed by the satisfaction question at the Month 12/early termination visit.

1.2.3 Safety Objectives

The safety objective is to evaluate the effect on safety endpoints of abobotulinumtoxinA in the treatment of glabellar lines.

1.3 Efficacy Assessments

For all assessments, baseline will be defined as the observation that is closest to but prior to study treatment on Day 0. Likewise, change from baseline will be calculated as the value at a given time point minus the baseline value.

1.3.1 Overall Subject Satisfaction by Direct Questioning

[REDACTED] The subject will document their response of Highly Satisfied, Satisfied, Dissatisfied, or Highly Dissatisfied.

1.4 Efficacy Endpoints

1.4.1 Primary Efficacy Endpoint

The primary endpoint will evaluate the proportion of subjects satisfied (“highly satisfied” or “satisfied”) with the treatment results assessed by the satisfaction question at the Month 12/early termination visit.

The figure consists of a 10x10 grid of black bars on a white background. The width of each bar in a row is determined by the value in the corresponding cell of a 10x10 matrix. The matrix values range from 1 to 10, with 10 being the widest bar and 1 being the narrowest. The bars are positioned such that they overlap slightly, and the grid lines are visible between the bars.

1.5 Safety Assessments

The methods for collecting safety data are described in Section 7.2 of the Clinical Study Protocol.

1.6 Safety Endpoints

Safety endpoints include:

(i) Treatment Emergent Adverse Events (TEAEs)

Adverse events (AEs) are to be monitored throughout the course of the study. The study period for the purpose of AE collection is defined as the period from the signing of a study specific informed

consent to study exit for a subject. AEs recorded on the electronic case report forms (eCRFs) will be coded using the Medical Dictionary for Regulatory Activities (MedDRA). AEs will be classified as treatment-emergent adverse events (TEAEs) if the AE had an onset time greater than or equal to the time of the dose of first study treatment.

Adverse events endpoints include:

- Incidence,
- Causality (related/not related to investigational product),
- Intensity (mild/moderate/severe),
- Leading to study withdrawal,
- Seriousness.

(ii) Focused Physical Examination

At all study visits (prior to treatment as applicable), the Investigator or designee will perform a physical examination of the subject that includes the face and neck. The Investigator may choose to investigate any other sign that he/she observes during the physical examination and should assess all abnormal findings for clinical significance.

2 Statistical Methods

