2.1.3 Safety Objectives and Endpoints

The safety objective of the study is to evaluate the safety of abobotulinumtoxinA in the treatment of glabellar lines.

The safety endpoint will include the incidence and severity of treatment emergent adverse events (TEAEs) throughout the study.

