3 OVERALL CLINICAL STUDY DESCRIPTION

This is a multicenter, open-label, interventional, phase 4 study to assess subject satisfaction with a twice-yearly abobotulinumtoxinA treatment regimen.

Following signature of informed consent and the screening process, eligible subjects will be treated at the baseline visit (Day 0) with abobt abobt ulinum toxinA in the glabellar region. Subjects will be re-treated at the month 6 visit,

Subjects will be monitored for up to 13 months following the initial treatment at baseline.

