8.1 Focused Physical Examination

At all study visits (prior to treatment, as applicable), the Investigator or designee will perform a physical examination of the subject that includes the face, head, and neck. Further details are provided in Appendix 4.

The Investigator may choose to investigate any other sign that he/she observes during the physical examination and should assess all abnormal findings for clinical significance.

Clinically significant abnormal findings at the screening/baseline visit are exclusionary, and the subject should not be enrolled in the study. If the abnormality is not clinically significant, capture it as medical history.

For any clinically significant changes from the screening/baseline visit, an AE is to be recorded.

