8.2 Adverse Events

AEs are to be monitored throughout the course of the clinical study from the time the informed consent form has been signed. All AEs are to be reported on the AE form of the eCRF with complete information as required.

If AEs occur, the main concern shall be the safety of the subjects. At the time of the ICF signature, each subject must be provided with the name and phone number of clinical study center personnel for reporting AEs and medical emergencies.

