8.2.1.1.2 Treatment Emergent Adverse Events (TEAE)

A TEAE is an event that emerges during treatment, having been absent pre-treatment, or worsens relative to the pretreatment state.

Investigators are responsible for monitoring, recording, and reporting all AEs that occur during the study as described. TEAEs will be delineated from AEs following database lock.

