8.2.1.1.5 Adverse Event Reporting Period

The clinical study period during which AEs must be reported is the period from when the subject signed the ICF to the end of the subject's participation.

The Sponsor should be informed if the Investigator becomes aware of any unusual safety information or any safety information that appears to be drug-related involving a subject who has participated in a clinical study, even after a subject has completed the clinical study.

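### SAP 1.6 flags TEAEs by onset alone and drops the protocol's worsening criterion, so an AE recorded before the first injection that worsens afterwards on the same record is left out of the TEAE tables

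*SAP*

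**What the plan says.** Protocol 8.2.1.1.2 describes a TEAE as an event that emerges during treatment, "having been absent pre-treatment, or worsens relative to the pretreatment state". It therefore has two criteria: new, or worse. The same section says that "TEAEs will be delineated from AEs following database lock".

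SAP 1.6 has one criterion. An AE is treatment-emergent "if the AE had an onset time greater than or equal to the time of the dose of first study treatment". The sentence is complete and unredacted, and no worsening rule appears elsewhere in the readable SAP.

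The term carries the safety endpoint. Protocol 2.1.3 states: "The safety endpoint will include the incidence and severity of treatment emergent adverse events (TEAEs) throughout the study".

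On precedence, SAP 2.1 lets the SAP override the protocol's statistical sections. The TEAE definition is in protocol Section 8, the safety assessments, and not in Section 10. SAP 2.8 reports no significant change from the protocol's planned analysis and does not mention the narrower rule.

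**The concern.** AEs are collected before anyone is treated. Protocol 8.2 says "AEs are to be monitored throughout the course of the clinical study from the time the informed consent form has been signed", and protocol Section 3 places consent and screening before the Day 0 injection. An AE can therefore be on record with an onset earlier than first treatment. If it becomes worse after the injection, the protocol calls it treatment-emergent. If the site updates the existing record rather than opening a new one, the SAP rule does not.

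Because TEAEs are separated from other AEs only after database lock, the programmed SAP rule decides the classification. What is at stake is the completeness of the TEAE incidence and severity tables. A worsening after injection is the kind of event that the protocol's second criterion exists to catch.

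**Working it through.** No formula applies, so the check is to run each definition over the possible AE patterns.

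| Pattern | Protocol 8.2.1.1.2 | SAP 1.6 |
|---|---|---|
| (a) New AE, onset at or after first treatment | TEAE | TEAE |
| (b) Medical-history condition that worsens after treatment and is entered as a new AE | TEAE | TEAE (onset is the date of worsening) |
| (c) AE with onset between consent and first treatment, no worsening | Not a TEAE | Not a TEAE |
| (d) AE with onset between consent and first treatment that worsens afterwards, same record and original onset date | TEAE | Not a TEAE |

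Only pattern (d) differs.

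**Can (d) occur?** It needs an AE recorded before injection. The reporting period in protocol 8.2.1.1.5 allows this: "The clinical study period during which AEs must be reported is the period from when the subject signed the ICF". It also needs the worsening to stay on the original record. The readable text does not say whether worsening of an AE already on the form becomes a new record or a change to the old one. The conflict in wording is therefore certain, and its effect on the tables is conditional.

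**How far would an affected event reach?** Counting the visible summaries in SAP 2.5.2, with redacted lines left out:

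- Overall summary: 6 rows. One covers all AEs. The other 6 − 1 = 5 are restricted to TEAEs (any, treatment-related, by intensity, leading to discontinuation, serious).
- Summaries by SOC and PT: 5 by maximum intensity or causality (all, serious, related, unrelated, leading to discontinuation), plus 1 for action taken, plus 1 for days to onset and duration. That gives 5 + 1 + 1 = 7, all restricted to TEAEs.

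These are counts of tables, not of events. Related and unrelated are mutually exclusive, so a single event could be missing from at most 7 − 1 = 6 of the SOC/PT summaries. It would still be counted in the all-AE row and shown in the listings promised by SAP 2.1.2.

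**Time to onset.** SAP 2.5.2 subtracts the date of the most recent treatment from the AE start date. A pattern (d) event has no treatment before its recorded start, so the derivation has no value for it. Adding the worsening criterion alone would leave this gap for related events.

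**How many events?** This cannot be derived. The documents give no AE rate, and the readable text gives no length for the interval from consent to injection.

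**The case against.** The best counter-argument is that data capture already delivers most of the worsening criterion. Protocol 8.2.1.1.1 makes clinically significant worsening of an existing condition, compared with the first visit, an AE in its own right. Protocol 8.1 requires an AE for clinically significant changes from screening/baseline. A worsening entered that way has an onset after treatment, and the SAP rule catches it.

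The exposed window also looks short. Protocol 5.2.2, 8.1 and the pregnancy-test paragraph treat screening and baseline as one occasion. Protocol 8.1 further narrows the class: "Clinically significant abnormal findings at the screening/baseline visit are exclusionary, and the subject should not be enrolled in the study", and findings that are not clinically significant go to medical history. A recording convention may sit in the data management plan (protocol 11.3) or in the redacted parts of SAP 2.5 and 2.5.2. Finally, SAP 2.8 denies only significant changes, and a sponsor could fairly regard this one as insignificant.

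Most of this stands, and it is why the point is minor. It does not remove the conflict. The AE rules cover medical-history conditions and separately entered worsening, but they do not say what happens to an AE already on the form. Protocol 5.5 and 8.2.1.2.3 refer to a screening period, so an interval before injection cannot be ruled out. Two different definitions of the safety endpoint's own term remain.

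**Conclusion.** The concern holds. SAP 1.6 is narrower than protocol 8.2.1.1.2, the precedence clause does not clearly cover the difference, and SAP 2.8 does not declare it. The consequence is confined to AEs that start between consent and first injection and worsen later on the same record. Probably very few events are involved, and the primary endpoint is not affected.

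This conclusion assumes that no worsening rule sits in the redacted SAP text, and that worsening of a recorded AE can stay on its original record. If an unseen convention requires a new record with a new onset date, the tables would come out right and only the mismatch in wording would remain. This is a tidy-up that is worth making, not a threat to the study's conclusions.

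**What to change.** 1. In SAP 1.6, define a TEAE as an AE that starts at or after first study treatment, or that starts earlier and worsens after first treatment relative to the pretreatment state. Keep the protocol's general sense of worsening and do not limit it to a change of intensity grade.
2. State how worsening of an already recorded AE is captured and dated, or cite the data management plan if the rule is there. The convention is needed before database lock, because the flag is derived afterwards.
3. In SAP 2.5.2, use the date of worsening for time to onset of related TEAEs that qualify by worsening.
4. If the sponsor keeps the onset-only rule, declare it in SAP 2.8 as a departure from protocol 8.2.1.1.2.

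The cost is one sentence in SAP 1.6, one line in SAP 2.5.2 and minor programming. The AE form items named in protocol 8.2.1.2.1 include onset date and severity but no date of worsening. If none is captured, a new data item or a site instruction to open a new record would also be needed. TEAE counts may be slightly higher.
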